## 10.2. Appendix 2: Data Display Standards & Handling Conventions

### 10.2.1. Reporting Process

Software	

 
The currently supported versions of SAS software will be used.
 
	
Reporting Area	
HARP Server	: UK1SALX00175
HARP Compound	: NOCOMPOUND\MID207654\Internal_01
Analysis Datasets	

 
Analysis datasets will be created per GSK IDSL dataset standards.
 
	
Generation of RTF Files	

 
RTF files will be generated for interim reporting effort.
 
	

### 10.2.2. Reporting Standards

General

 
The current GSK Integrated Data Standards Library (IDSL) will be applied for reporting, unless otherwise stated (IDSL Standards Location: https://spope.gsk.com/sites/IDSLLibrary/SitePages/Home.aspx):             
 
4.03 to 4.23: General Principles
 
5.01 to 5.08: Principles Related to Data Listings
 
6.01 to 6.11: Principles Related to Summary Tables
 
7.01 to 7.13: Principles Related to Graphics
 
 
 
All displays will use the term "Subject", the term "Subject" is used to refer to a participant in the protocol.
 
Do not include subject level listings in the main body of the GSK Clinical Study Report. All subject level listings should be in the modular appendices as ICH or non-ICH listings
 

Formats

 
GSK IDSL Statistical Principles (5.03 & 6.06.3) for decimal places (DP's) will be adopted for reporting of data based on the raw data collected, unless otherwise stated.
 
Numeric data will be reported at the precision collected on the eCRF.
 
The reported precision from non eCRF sources will follow the IDSL statistical principles but may be adjusted to a clinically interpretable number of DP's.             
 
For all Biomarkers, the following DP's places will be applied:
 
Summary Statistics: Maximum of 4 DP's for Mean and Median, 5 DP's for SD, 3 DP's for Min and Max.
 
Listings: Provide DP's in BEST. format.
 
 
 

Planned and Actual Time

 
Reporting for tables, figures and formal statistical analyses:             
 
Planned time relative to dosing will be used in figures, summaries, statistical analyses and calculation of any derived parameters, unless otherwise stated.
 
The impact of any major deviation from the planned assessment times and/or scheduled visit days on the analyses and interpretation of the results will be assessed as appropriate.
 
 
 
Reporting for Data Listings:             
 
Planned and actual time relative to study drug dosing will be shown in listings (Refer to IDSL
 
 
 

Statistical Principle 5.05.1). 
 
• Unscheduled or unplanned readings will be presented within the subject's listings.
 
	
Unscheduled Visits	

 
• Unscheduled visits will not be included in summary tables and/or figures.
 
• All unscheduled visits will be included in listings.
 
	
Descriptive Summary Statistics	
Continuous Data	Refer to IDSL Statistical Principle 6.06.1
Categorical Data	N, n, frequency, %
Graphical Displays	

 
• Refer to IDSL Statistical Principals 7.01 to 7.13.
 
	

### 10.3. Appendix 3: Derived and Transformed Data

#### 10.3.1. General

Multiple Measurements at One Analysis Time Point

 
• Mean of the measurements will be calculated and used in any derivation of summary statistics but if listed, all data will be presented.
 
• If there are two values within a time window the value closest to the target day for that window will be used. If values are the same distance from the target, then the mean will be taken.
 
• Participants having both High and Low values for Normal Ranges at any post-baseline visit for safety parameters will be counted in both the High and Low categories of “Any visit post-baseline” row of related summary tables. This will also be applicable to relevant Potential Clinical Importance summary tables.
 
• For the biomarkers from skin blister fluid, values will be averaged across arms (left and right) for each participant. These averaged values will be used in tables and figures. If one of the values is not collected or is missing, then the single value present in the data will be used in tables and figures. Appropriate footnotes will be provided to reflect data are not an average value.
 

Study Day

 
• Calculated as the number of days from Challenge Administration Date:                             
 
• Ref Date = Missing → Study Day = Missing
 
• Ref Date < Challenge Administration Date → Study Day = Ref Date - Challenge Administration Date
 
• Ref Date ≥ Challenge Administration Date → Study Day = Ref Date - (Challenge Administration Date) + 1
 
 
 

#### 10.3.2. Study Population

Age

 
• GSK standard IDSL algorithms will be used for calculating age where birth date will be imputed as follows:
 
• Any participant with a missing day will have this imputed as day ‘15’.
 
• Any participant with a missing date and month will have this imputed as ‘30th June’.
 
• Birth date will be presented in listings as ‘YYYY’.
 
• If only birth year is collected, then the birth date and month will be imputed as ‘30th June’ for calculating age.
 
• The reference day for age calculation will be screening visit.
 

#### 10.3.3. Biomarker

The table below provides the list of Biomarkers needed for Interim.

Biomarker Code (BICATCD), Biomarker Test Code (BITESTCD), Biomarker Testing Method Code (BIMETHCD) and Units of Measurement (BIORRESU) can be referred below.

Name (Analyte)	Biomarker Detailed Name	BICATCD	BITESTCD/ BIMETHCD/ BIORRESU
Soluble Inflammatory Mediators (Blood) Primary	Tumour necrosis factor alpha (TNF- $\alpha$ )	TNFA	CONC/ MSD/ PG/ML
	Interleukin 6	IL6	CONC/ MSD/ PG/ML
Soluble Inflammatory Mediators (Blood) Secondary	C-reactive protein (LAB dataset)	LBTESTCD: CRP_PLC	LBORUNIT: MG/L
	Monocyte chemotactic protein-1	MCP1	CONC/ MSD/ PG/ML
	Monocyte chemotactic protein-4	MCP4	CONC/ MSD/ PG/ML
	Eotaxin	EOTAXIN	CONC/ MSD/ PG/ML
	Inducible protein 10	IP10	CONC/ MSD/ PG/ML
	MDC	MDC	CONC/ MSD/ PG/ML
	Chemokine (C-C motif) ligand 26 gene	CCL26	CONC/ MSD/ PG/ML
	Thymus and activation-regulated chemokine	TARC	CONC/ MSD/ PG/ML
	Macrophage inflammatory protein 1 alpha	MIP1A	CONC/ MSD/ PG/ML
	Macrophage inflammatory protein 1 beta	MIP1B	CONC/ MSD/ PG/ML
	Interferon-gamma	IFNG	CONC/ MSD/ PG/ML
	Interleukin 10	IL10	CONC/ MSD/ PG/ML
	Interleukin 12 p70	IL12P70	CONC/ MSD/ PG/ML

Name (Analyte)	Biomarker Detailed Name	BICATCD	BITESTCD/ BIMETHCD/ BIORRESU
	Interleukin 1 beta	IL1B	CONC/ MSD/ PG/ML
	Interleukin 8	IL8	CONC/ MSD/ PG/ML
	Activin-A	ACTIVA	CONC/ ELISA/ PG/ML
	Matrix metalloproteinase-1 (interstitial collagenase)	MMP1	CONC/ MSD/ PG/ML
	Matrix metalloproteinase 3	MMP3	CONC/ MSD/ PG/ML
	Matrix metalloproteinase 9	MMP9	CONC/ MSD/ PG/ML
	Granulocyte macrophage colony stimulating factor	GMCSF	CONC/ ELISA/ PG/ML
Soluble Inflammatory Mediators (Blood - TruCulture)	Interleukin 10	IL10	CONC/ MSD/ PG/ML
	Interleukin 6	IL6	CONC/ MSD/ PG/ML
	Interleukin 8	IL8	CONC/ MSD/ PG/ML
	Tumour necrosis factor alpha (TNF- $\alpha$ )	TNFA	CONC/ MSD/ PG/ML
	Chemokine (C-X-C motif) ligand 1 (melanoma growth stimulating activity, alpha)	CXCL1	CONC/ ELISA/ PG/ML
Soluble Inflammatory Mediators (Blister)	Monocyte chemotactic protein-1	MCP1	CONC/ MSD/ PG/ML
	Interleukin 10	IP10	CONC/ MSD/ PG/ML
	Thymus and activation-regulated chemokine	TARC	CONC/ MSD/ PG/ML

Name (Analyte)	Biomarker Detailed Name	BICATCD	BITESTCD/ BIMETHCD/ BIORRESU
	Interleukin 12 p70	IL12P70	CONC/ MSD/ PG/ML
	Activin-A	ACTIVA	CONC/ ELISA/ PG/ML
	Matrix metalloproteinase-1 (interstitial collagenase)	MMP1	CONC/ MSD/ PG/ML
	Matrix metalloproteinase 3	MMP3	CONC/ MSD/ PG/ML
	Matrix metalloproteinase 9	MMP9	CONC/ MSD/ PG/ML
Soluble Inflammatory Mediators (Urine) Primary	Tetranor-Prostaglandin E Metabolite	TETPGDM	CONC/ LCMS/ PG/ML
	Tetranor-Prostaglandin D Metabolite	TETPGEM	CONC/ LCMS/ PG/ML
Cell Numbers (Blood) Primary	White blood cells	WBC	TNCELL/ FLWCY/ CELLS/ML
Blister Volume (Blister)	Blister Fluid	BLISTFL	VOL/ WTDENC/ UL
Flow Cytometry  Cell Activation Markers on Monocytes (Blister and Blood)	CD16+	CD16	C6/ FLWCY/ MNFI
	CD86+	CD86	C6/ FLWCY/ MNFI
	CD80 molecule	CD80	C6/ FLWCY/ MNFI
	CD163+	CD163	C6/ FLWCY/ MNFI
	CD206+	CD206	C6/ FLWCY/ MNFI
	CD83 molecule	CD83	C6/ FLWCY/ MNFI

Name (Analyte)	Biomarker Detailed Name	BICATCD	BITESTCD/ BIMETHCD/ BIORRESU
	CD40	CD40	C6/ FLWCY/ MNFI
	CD209+	CD209	C6/ FLWCY/ MNFI
	HLA-DR	HLADR	C6/ FLWCY/ MNFI
	CD40+/CD80+	CDX690	%MONO/ FLWCY/ %
Flow Cytometry  Cell Activation Markers on Dendritic Cells  (Blister and Blood)	CD16+	CD16	R1/ FLWCY/ MNFI
	CD86+	CD86	R1/ FLWCY/ MNFI
	CD80 molecule	CD80	R1/ FLWCY/ MNFI
	CD163+	CD163	R1/ FLWCY/ MNFI
	CD206+	CD206	R1/ FLWCY/ MNFI
	CD83 molecule	CD83	R1/ FLWCY/ MNFI
	CD40	CD40	R1/ FLWCY/ MNFI
	CD209+	CD209	R1/ FLWCY/ MNFI
	HLA-DR	HLADR	R1/ FLWCY/ MNFI
CD40+/CD80+	CDX690	%TDC/ FLWCY/ %	
Flow Cytometry	Neutrophils	NEUT	TNCELL/ FLWCY/ CELLS/ML

Name (Analyte)	Biomarker Detailed Name	BICATCD	BITESTCD/ BIMETHCD/ BIORRESU
Cell Counts (Blood)	Lymphocytes	LYMPH	TNCELL/ FLWCY/ CELLS/ML
	Monocytes	MONO	TNCELL/ FLWCY/ CELLS/ML
	B Cells	BCELL	TNCELL/ FLWCY/ CELLS/ML
	CD45+ CD3- CD56+ (NK Cells)	CDX223	TNCELL/ FLWCY/ CELLS/ML
	CD45+ CD3+ CD56+ (NKT Cells)	CDX224	TNCELL/ FLWCY/ CELLS/ML
	Total T Cells	TTCELL	TNCELL/ FLWCY/ CELLS/ML
	CD4+	CD4	TNCELL/ FLWCY/ CELLS/ML
	CD8+	CD8	TNCELL/ FLWCY/ CELLS/ML
	CD14+CD16+ Monocytes	CDX469	TNCELL/ FLWCY/ CELLS/ML
	CD14+CD16- Monocytes	CDX471	TNCELL/ FLWCY/ CELLS/ML
	CD14-CD16+ Monocytes	CDX611	TNCELL/ FLWCY/ CELLS/ML
Flow Cytometry  Cell Counts (Blister)	Neutrophils	NEUT	TNCELL/ FLWCY/ CELLS/ML or 10  CELLS/BLISTER
Note: These biomarkers are measured in 2 units –	Lymphocytes	LYMPH	TNCELL/ FLWCY/ CELLS/ML or 10  CELLS/BLISTER

Name (Analyte)	Biomarker Detailed Name	BICATCD	BITESTCD/ BIMETHCD/ BIORRESU
Cells/ml and 10  Cells/Blister	Monocytes	MONO	TNCELL/ FLWCY/ CELLS/ML or 10  CELLS/BLISTER
	B Cells	BCELL	TNCELL/ FLWCY/ CELLS/ML or 10  CELLS/BLISTER
	CD45+ CD3- CD56+ (NK Cells)	CDX223	TNCELL/ FLWCY/ CELLS/ML or 10  CELLS/BLISTER
	CD45+ CD3+ CD56+ (NKT Cells)	CDX224	TNCELL/ FLWCY/ CELLS/ML or 10  CELLS/BLISTER
	Total T Cells	TTCELL	TNCELL/ FLWCY/ CELLS/ML or 10  CELLS/BLISTER
	CD4+	CD4	TNCELL/ FLWCY/ CELLS/ML or 10  CELLS/BLISTER
	CD8+	CD8	TNCELL/ FLWCY/ CELLS/ML or 10  CELLS/BLISTER
	CD14+CD16+ Monocytes	CDX469	TNCELL/ FLWCY/ CELLS/ML or 10  CELLS/BLISTER
	CD14+CD16- Monocytes	CDX471	TNCELL/ FLWCY/ CELLS/ML or 10  CELLS/BLISTER

Name (Analyte)	Biomarker Detailed Name	BICATCD	BITESTCD/ BIMETHCD/ BIORRESU
	CD14-CD16+ Monocytes	CDX611	TNCELL/ FLWCY/ CELLS/ML or 10  CELLS/BLISTER

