3.3.3. Pharmacokinetics and pharmacodynamics of GM-CSF

When GM-CSF (also known as sargramostim) is administered to patients by intravenous infusion over 2 hours, it reaches a mean beta half-life of approximately 60 minutes. The peak concentrations of GM-CSF are observed in blood samples obtained during or immediately after completion of the sargramostim infusion, while minor concentrations are still detected in blood 6 hours after the beginning of the infusion. GM-CSF is also detected in serum first after 15 minutes of subcutaneous injection of sargramostim to healthy volunteers. Then, the mean beta half-life is approximately 162 minutes, and peak levels are reached after one to 3 hours post-injection and remain detectable for up to 6 hours.

Sargramostim is usually well tolerated by healthy participants, who have not shown clinical alterations in their clinical analysis, as compared to placebo-treated individuals. (Francisco-Cruz, 2014)

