4. OBJECTIVES AND ENDPOINTS

[figure not shown]
Objective	Endpoint	
Primary		
• To compare and define the time course of soluble and cellular inflammatory biomarkers (and urinary prostaglandins for LPS only) following systemic challenge with LPS or GM-CSF in healthy participants	 For LPS only: time course and magnitude of upregulation of circulating TNF-α and IL-6 as well as urinary tetranor PGDM. For GM-CSF only: time course and magnitude of upregulation of circulating total leukocyte numbers 	
Secondary		
• To compare soluble and cellular inflammatory biomarkers in cantharidin-induced skin blisters at baseline versus systemic challenge with LPS or GM-CSF in healthy participants	 Soluble inflammatory biomarkers in skin blisters (may include but not limited to IL-1b, IL-2, IL-6, IL-8, IFNg, TNF-α, MCP-1, GM- CSF, CRP). Blister volumes and differential cell counts (cellular activation markers may include, but not limited to expression of CD16, CD86, CD80, CD163, CD206, CD83, CD40, CD209, HLA-DR in blister leukocytes) 	

Objective	Endpoint		
• To define the time course of circulating soluble and cellular inflammatory biomarker upregulation following systemic challenge with LPS or GM-CSF in healthy participants	 Time course of regulation of circulating soluble inflammatory biomarkers (may include but is not limited to IL-1b, IL-2, IL-6, IL-8, IFNg, TNF-α, MCP-1, GM-CSF, CRP). Time course of regulation of 		
	circulating leukocyte numbers and cellular activation markers (may include, but not limited to expression of CD16, CD86, CD80, CD163, CD206, CD83, CD40, CD209, HLA-DR in circulating leukocytes)		
Exploratory			
• To compare suitability of blisters sampled at 24 and 48 hours after induction for maximising observed effects of systemic challenge	• Primary and Secondary endpoints measured in 24 versus 48 hour blisters		
• To assess the safety and tolerability profile of the challenge agents and to ensure it is not materially different from previous experience (as described in Section 3.2)	• Adverse events, clinical laboratory measures, vital signs, pain scale assessments		
• Determining whether carboxyesterase-1 (CES-1) expression is present in monocytes following systemic GM-CSF challenge	 Number of monocytes which are CES-1+ in blood 		

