9.5. Pharmacokinetics

Pharmacokinetics are not evaluated in this study.

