### 7.2.2. Summary Measure

Absolute values and change from baseline of soluble and cellular inflammatory biomarkers across the time course.

Note: In the Interim Analysis, for the biomarkers from skin blister fluid, values will be averaged across arms (left and right) for each participant. These averaged values will be used in tables and figures.

If one of the values is not collected or is missing, then the single value present in the data will be used in tables and figures. Appropriate footnotes will be provided to reflect data are not an average value.

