## 10.7.4. Biomarker Tables

Biomarker Tables					
No.	Population	IDSL / Example Shell	Title	Programming Notes	Deliverable [Priority]
Soluble Inflammatory Mediators					
2.1.	Safety	BIO_T1	Summary of Primary Soluble Inflammatory Mediators in Blood	Page by Treatment and Biomarker	IA [1]
2.2.	Safety	BIO_T1	Summary of Change from Baseline in Primary Soluble Inflammatory Mediators in Blood	Page by Treatment and Biomarker.	IA [1]
2.3.	Safety	BIO_T1	Summary of Secondary Soluble Inflammatory Mediators in Blood	Page by Treatment and Biomarker	IA [1]
2.4.	Safety	BIO_T1	Summary of Change from Baseline in Secondary Soluble Inflammatory Mediators in Blood	Page by Treatment and Biomarker	IA [1]
2.5.	Safety	BIO_T1	Summary of Soluble Inflammatory Mediators from In-Vitro (un)stimulated Blood Pre and Post In-Vivo LPS Challenge	Page by Treatment and Biomarker	IA [1]
2.6.	Safety	BIO_T1	Summary of Soluble Inflammatory Mediators in Blister	Page by Treatment and Biomarker	IA [1]
2.7.	Safety	BIO_T1	Summary of Change from Baseline of Soluble Inflammatory Mediators in Blister	Page by Treatment and Biomarker	IA [1]
2.8.	Safety	BIO_T1	Summary of Soluble Inflammatory Mediators in Urine following LPS Challenge	Page by Treatment and Biomarker	IA [1]
2.9.	Safety	BIO_T1	Summary of Change from Baseline of Soluble Inflammatory Mediators in Urine following LPS Challenge	Page by Treatment and Biomarker	IA [1]
Total Leukocyte Numbers					
2.10.	Safety	BIO_T1	Summary of Cell Numbers in Blood following GM-CSF Challenge	Page by Treatment and Biomarker	IA [1]
2.11.	Safety	BIO_T1	Summary of Change from Baseline in Cell Numbers in Blood	Page by Treatment and	IA [1]

Biomarker Tables					
No.	Population	IDSL / Example Shell	Title	Programming Notes	Deliverable [Priority]
			following GM-CSF Challenge	Biomarker	
Blister Volume					
2.12.	Safety	BIO_T1	Summary of Blister Volume	Page by Treatment	IA [1]
Flow Cytometry					
2.13.	Safety	BIO_T1	Summary of Cell Activation Markers by Flow Cytometry on Monocytes in Blood	Page by Treatment and Biomarker	IA [1]
2.14.	Safety	BIO_T1	Summary of Change from Baseline in Cell Activation Markers by Flow Cytometry on Monocytes in Blood	Page by Treatment and Biomarker	IA [1]
2.15.	Safety	BIO_T1	Summary of Cell Activation Markers by Flow Cytometry on Dendritic Cells in Blood	Page by Treatment and Biomarker	IA [1]

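### In the GM-CSF arm, GM-CSF readings after the challenge on Session 2 Day 1 are dominated by the infused drug, so their change from baseline cannot be read as inflammatory upregulation

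*SAP*

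**What the plan says.** Protocol section 4 sets this secondary objective: "To define the time course of circulating soluble and cellular inflammatory biomarker upregulation following systemic challenge with LPS or GM-CSF in healthy participants". The endpoint's indicative list of circulating soluble markers ends with "MCP-1, GM- CSF, CRP", and the same list serves both challenges.

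SAP 10.3.3 turns the indicative list into a definite one for the interim. "Granulocyte macrophage colony stimulating factor" appears there as a secondary blood mediator, measured by ELISA in pg/mL, with no restriction by arm. SAP 7.2.2 gives the summary measure: "Absolute values and change from baseline of soluble and cellular inflammatory biomarkers across the time course". The displays are Tables 2.3 and 2.4 (the latter titled "Summary of Change from Baseline in Secondary Soluble Inflammatory Mediators in Blood") and Figures 2.5 to 2.8. None of them is limited to one challenge. Other displays are limited, for example Table 2.10, "Summary of Cell Numbers in Blood following GM-CSF Challenge".

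For blood biomarkers outside the primary set, SAP 5.2 takes Session 1 Day 1 as baseline, before any challenge agent is given.

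On the drug, Protocol 3.3.3 treats GM-CSF and sargramostim as one substance. After a 2-hour intravenous infusion it places the peak blood level during the infusion or right at its end, gives a half-life of about 60 minutes, and adds that "minor concentrations are still detected in blood 6 hours after the beginning of the infusion". Protocol 9.5 says: "Pharmacokinetics are not evaluated in this study".

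**The concern.** In the GM-CSF arm the analyte and the challenge agent are the same molecule. The first post-challenge draws come soon after the infusion ends, when the drug level is near its highest, and baseline was taken when no drug was present. Change from baseline at those draws therefore contains the infused dose. The displays would present a drug-elimination curve under a title and an objective that speak of inflammatory mediators and their upregulation.

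Three uses of the data are exposed:

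- **The secondary endpoint.** Its time course in this arm would be misread on Day 1.
- **The Part II decision for GM-CSF.** SAP 3.2 says the available data on all biomarkers are weighed, alongside the leukocyte criterion.
- **The rule for dropping analytes.** SAP 3.2 drops a biomarker from Part II only if it is below the quantification limit at every time point in every Part I participant at the optimal dose. Infused drug alone can keep GM-CSF on the list, even if no endogenous GM-CSF is ever seen.

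In addition, SAP 10.4.2 omits values above the upper quantification limit from summaries and figures. That limit is not given. If the early drug readings exceed it, the interim displays would lose the top of the curve and keep the tail.

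**Working it through.** The plan states no figure for infused drug at the sampling times, so there is none to reproduce. The check uses first-order decay from the protocol's own half-life.

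**Inputs**

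- Half-life: about 60 min (Protocol 3.3.3).
- Infusion: about 2 h (Protocol 7.1).
- Cantharidin application: 20 min after the end of the challenge (Protocol section 2).
- Mediator draws: scheduled from blister induction (Protocol section 2, footnote 7). The 5-minute draw is read as 5 min before induction, as in the SAP mock table.
- Days 2 and 3: draws before blister sampling at 24 h and 48 h.
- Dose: 60 ug/m2 (SAP 3.2). Body surface area: 1.9 m2 (Protocol 5.5.3).

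**Step 1. Share of the end-of-infusion level remaining.** With t in minutes after the end of infusion, share = 2^(-t/60), where t = scheduled time + 20.

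| Draw, from blister induction | t (min) | Share remaining |
|---|---|---|
| -5 min | 15 | 84% |
| 10 min | 30 | 71% |
| 25 min | 45 | 59% |
| 40 min | 60 | 50% |
| 1 h 10 | 90 | 35% |
| 1 h 40 | 120 | 25% |
| 2 h 40 | 180 | 12.5% |
| 5 h 40 | 360 | 1.6% |
| 24 h | 1,460 | 5 x 10^-8 (fraction) |
| 48 h | 2,900 | 3 x 10^-15 (fraction) |

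**Step 2. Check against the protocol's own description.** Six hours after the start of infusion is 4 h (240 min) after its end: 2^(-240/60) = 6.25%. That fits the small residual level described in Protocol 3.3.3.

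**Step 3. Sensitivity to the half-life (assumed range 30 to 120 min).**

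| Half-life | 15 min | 60 min | 180 min | 360 min | 24 h draw |
|---|---|---|---|---|---|
| 30 min | 71% | 25% | 1.6% | 0.02% | effectively nil |
| 120 min | 92% | 71% | 35% | 12.5% | 0.02% |

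The early draws carry most of the drug, and the 24 h draw carries almost none, at either end of the range.

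**Step 4. Rough absolute size.** Dose = 60 x 1.9 = 114 ug. With one compartment, k = ln2/60 and T = 120 min, so kT = 1.386. Amount in the body at the end of infusion = 114 x (1 - e^(-1.386))/1.386 = 114 x 0.541 = 61.7 ug. The documents give no distribution volume. Assuming 5 to 50 L, the drug alone gives:

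- end of infusion: 12,300 to 1,230 pg/mL;
- first draw (x 0.841): about 10,400 to 1,040 pg/mL;
- 6 h after the end (x 0.0156): about 193 to 19 pg/mL.

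The shares in Step 1 do not depend on this volume. The pg/mL values do.

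**The case against.** The case for leaving the plan alone has several parts.

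- **The list is only indicative.** The protocol endpoint says what may be measured. That is true of the protocol, but SAP 10.3.3 makes the analyte definite for the interim.
- **The missing restriction may not be an oversight.** Tables 2.1-2.2 also carry no restriction by arm, although TNF-alpha and IL-6 are primary for LPS only. This stands: the documents do not show whether the omission was deliberate. Its effect on the reading is the same either way.
- **The assay may not read sargramostim.** Its specificity is not described. This stands as an assumption. Protocol 3.3.3 reports the infused product as GM-CSF detected in blood, so the inference is reasonable.
- **The model is simple.** One compartment with a terminal half-life ignores any earlier distribution phase, and the volume is assumed. The pg/mL values are therefore only a rough range.
- **The displays are descriptive, and this SAP covers only dose escalation and the interim.** Both points are true and limit the seriousness. The interim is nevertheless where the Part II decision is made.

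A reader might go further than the documents allow:

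- That GM-CSF in this arm never reflects inflammation. The 24 h and 48 h values contradict this, and some endogenous GM-CSF on Day 1 cannot be ruled out.
- That the plan sets the two arms side by side for this analyte. It does not. Tables 2.3-2.4 and Figures 2.5-2.6 page by treatment and biomarker, Figures 2.7-2.8 page by challenge and biomarker, and no between-arm contrast is planned.
- That GM-CSF will show one of the largest rises in its arm. The documents give no expected size for the other analytes there, so no ranking is possible.

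**Conclusion.** The point holds for the eight post-challenge draws on Session 2 Day 1, in blood, in the GM-CSF arm. At those draws, 84% falling to 1.6% of the end-of-infusion drug level is still present, and the plan would report it within a change from a drug-free baseline. Those changes cannot be read as inflammatory upregulation.

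Two assumptions carry the conclusion: the ELISA reads sargramostim, and elimination is close to the half-life the protocol gives. The percentages are shares of the end-of-infusion level, not of the reading. The documents give no endogenous level, so the exact split is unknown. Dominance of the drug is most secure at the early draws and least secure at 6 h, where the firmer statement is that drug and response cannot be separated.

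Session 1, pre-challenge, 24 h and 48 h values in this arm, and all GM-CSF values in the LPS arm, remain valid as biomarker data. The primary endpoints and the numeric leukocyte criterion for Part II are not affected. The change is worth making because the plan as written misstates part of a secondary endpoint and the correction is cheap. It is not critical to the study.

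**What to change.** Add one line to SAP 10.3.3 and one programming note, applying to the GM-CSF arm only:

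- Label GM-CSF values from the Session 2 Day 1 post-challenge draws as circulating challenge-agent concentration wherever absolute values are shown (Table 2.3, Figures 2.5 and 2.7).
- Exclude those values from the change-from-baseline displays (Table 2.4, Figures 2.6 and 2.8).
- Exclude them from the biomarker evidence for Part II and from the detectability rule in SAP 3.2.
- Keep the Session 1, pre-challenge, 24 h and 48 h values as planned.

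GM-CSF stays a response marker at all times in the LPS arm. Carry the same note into the later SAP version for final reporting.

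No new samples or assays are needed. The label does not create a pharmacokinetic endpoint, and there is no draw during the infusion to support one. The one loss is that endogenous GM-CSF on Day 1 in this arm is not reported as a response, but it could not be separated from the drug in any case.

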9.7.2. Biomarkers in urine

The pre-challenge urine sample will be collected during session 1. The post-challenge urine samples will be collected during session 2 after LPS challenge. In session 2, participants will be encouraged to pass urine immediately before LPS challenge dose and urine voids will be collected from after LPS until 12 hours post-LPS and the time of the urine collection will be recorded. These samples will be collected for measurement of tetranor-PGDM and other inflammatory mediators. Tetranor-PGDM is the stable urinary metabolite of the prostaglandin PGD2. While tetranor-PGDM has very low natural abundance in normal healthy individuals, it has been shown to be elevated in the urine of patients with Duchenne muscular dystrophy. Elevation of urinary tetranor-PGDM in normal healthy volunteers through LPS challenge would allow for evaluation of target engagement in that population Tetranor-PGDM and related metabolite will be measure by mass spectroscopy as samples are collected.

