
 
To assess the safety and tolerability profile of the challenge agents and to ensure it is not materially different from previous experience.
 
	
 
Adverse events, clinical laboratory measures, vital signs, pain scale assessments
 

 
Determining whether carboxyesterase-1 (CES-1) expression is present in monocytes following systemic GM-CSF challenge
 
	
 
Number of monocytes which are CES-1+ in blood
 

 
To compare prostaglandins in urine, blister fluid and plasma at baseline versus systemic challenge with LPS or GM-CSF
 
	
 
Quantification of prostaglandins including (but not limited to ) tetranor -PGDM, tetranor-PGEM, PGD2 and PGE2
 

 
To assess changes in whole blood transcriptome induced by systemic LPS or GM-CSF
 
	
 
Analysis of differential gene expression in whole blood taken pre-challenge and at selected times post- challenge
 

 
For LPS challenge only: to assess whether the dose of in -vivo LPS challenge is sufficient to induce innate immune tolerance
 
	
 
Quantification of inflammatory markers including (but not limited to) TNF-<math>\alpha</math> and IL-6 in blood drawn pre- and 6 hour post-systemic LPS challenge following ex vivo incubation in 'LPS-TruCulture' tubes and LPS-null TruCulture'
 

Objectives	Endpoints

 
To assess the effects of systemic LPS and GM-CSF challenges on blister healing times
 
	tubes  
 
Blister healing times (self-reported in participant diary card)
 

[1] As an exploratory endpoint, samples will be measured in the Somalogics assay. [2] Blister samples will also be used in the Somalogics assay. [3] Protein panels: IL-6, TNF- $\alpha$ (tolerized proteins), GRO-a (CXCL1) (unchanged) & IL-8 & IL-10 (hyper-responsive)	

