#### 7.1.1. Endpoint / Variables

Challenge	Endpoint
LPS	Time course and magnitude of upregulation of circulating TNF- $\alpha$ and IL-6 as well as urinary tetranor PGDM
GM-CSF	Time course and magnitude of upregulation of circulating total leukocyte numbers.

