### 7.2.1. Endpoint / Variables

There are several different types of biomarker samples collected during the study:

- Biomarkers from skin blister fluid (i.e. mediators and flow cytometry)
- Biomarkers from blood sample (i.e. mediators, flow cytometry, ex vivo stimulation (LPS only) and transcriptome)
- Biomarkers from urine (Primary endpoints)

The secondary endpoints of interest with respect to the biomarkers mentioned above:

Endpoint
Soluble and cellular inflammatory biomarkers in cantharidin-induced skin blisters at baseline versus systemic challenge with LPS or GM-CSF in healthy participants
Time course of circulating soluble and cellular inflammatory biomarker upregulation

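### The SAP's biomarker code table crosses the D and E prostaglandin metabolites in urine and files both as primary, so the urinary primary endpoint can be mislabelled or, if selected by name, taken from the wrong analyte

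*SAP*

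**What the plan says.** SAP 10.3.3 gives the list of biomarkers needed for the interim, with a long name, a category code and the test, method and unit for each. SAP 3.2 points to that list for the content of the interim tables and figures.

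Under the heading "Soluble Inflammatory Mediators (Urine) Primary" the list has two rows: "Tetranor-Prostaglandin E Metabolite TETPGDM" and "Tetranor-Prostaglandin D Metabolite TETPGEM". Protocol 9.7.2 states: "Tetranor-PGDM is the stable urinary metabolite of the prostaglandin PGD2".

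The LPS primary endpoint in SAP 7.1.1 is circulating TNF-alpha and IL-6 "as well as urinary tetranor PGDM". Tetranor-PGEM appears only in the exploratory prostaglandin endpoint of SAP 2.2, which lists "tetranor -PGDM, tetranor-PGEM, PGD2 and PGE2". SAP 7.2.1 nevertheless describes the urine samples as a group: "Biomarkers from urine (Primary endpoints".

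In the blister block of the same table, one row reads "Interleukin 10 IP10". In the blood block, IP10 is the code for Inducible protein 10, and Interleukin 10 has its own code, IL10.

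**The concern.** Tetranor-PGDM is one of three LPS primary endpoints and one of the three conditions in the LPS rule for opening Part II. It is also the marker that the protocol ties to Duchenne muscular dystrophy and to target engagement. In the table that specifies the interim displays, its name and its code point to different mediators.

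A programmer or reader who relies on one column gets a different analyte from one who relies on the other. The filing of both rows as primary removes the tier label as a way to tell them apart. The blister row raises the same question for one more mediator. SAP 3.2 also drops from Part II any biomarker that was below quantification throughout Part I at the optimal dose, and that rule depends on knowing which analyte each row holds.

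**Working it through.** No arithmetic is involved; the check sets the entries side by side.

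**1. The urine rows.**

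| Code (SAP 10.3.3) | Long name in that row | Meaning from the protocol and endpoint tables | Tier in SAP 10.3.3 | Tier in SAP 2.2 and 7.1.1 |
|---|---|---|---|---|
| TETPGDM | E metabolite | D metabolite (protocol 9.7.2) | Primary | Primary |
| TETPGEM | D metabolite | E metabolite (by elimination, and by its own letters) | Primary | Exploratory only |

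The name contradicts the code in 2 of 2 rows, and 1 of the 2 analytes filed as primary is not a primary endpoint. SAP Table 1, which records changes from the protocol's analysis, does not promote tetranor-PGEM.

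**2. Whether anything else in the table resolves it.** Both rows carry the same test, method and unit (concentration, LC-MS, pg/mL). Name and code are the only identifiers, and they conflict.

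**3. The blister row.** Blood: IP10 is Inducible protein 10 and IL10 is Interleukin 10. Blister: IP10 is Interleukin 10. All three rows are concentration by MSD in pg/mL, so again nothing else separates them.

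**4. What follows for the displays.** The urine results go to Tables 2.8 and 2.9, Figures 2.15 to 2.18 and Listing 6. The tables and figures are paged by biomarker, and the listing shell has a biomarker column. Assume that the codes in the dataset are right:

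- Selecting by code TETPGDM gives the right values, which can be printed under the E-metabolite name.
- Selecting by the D-metabolite name leads to code TETPGEM, so tetranor-PGEM values stand in for the primary urinary endpoint.

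**5. What follows for Part II.** SAP 3.2 opens the LPS part if at least one participant meets all three conditions: TNF-alpha increase below 50 pg/mL, AND IL-6 increase below 50 pg/mL, AND tetranor-PGDM increase below 1.3x.

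| Both cytokine conditions met? | Urinary analyte used | Effect on that participant's result |
|---|---|---|
| No | Either | None; the rule already fails |
| Yes | PGDM (by code) | None; the right analyte decides |
| Yes | PGEM (by name) | Wrong if PGDM and PGEM fall on opposite sides of 1.3x |

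**6. What follows for dose escalation.** SAP 3.1 says that those reviews used raw tetranor-PGDM data from the sponsor's laboratory group, with graphs made in Excel. It does not refer to the codes in SAP 10.3.3.

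**The case against.** The strongest reply is that the SAP calls the endpoint PGDM wherever it defines it or sets a criterion: sections 2.2, 3.1, 3.2, 7.1.1 and 7.1.2. That string matches the code TETPGDM, and a programmer working by code would take the right values. Both analytes are displayed, so no result is lost. Nothing states that laboratory results are decoded, or page labels generated, from the long-name column. The interim is descriptive, with no hypotheses and no multiplicity adjustment, and the urine display titles do not use the word primary. A separate plan for the final report is to follow.

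Much of this stands, and it limits the consequence. It does not remove the error: the table is the specification to which SAP 3.2 refers, and no other text corrects it.

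A reader might infer more: that the primary urinary result will be wrong whichever route is taken, or that the Part II decision and the chosen LPS dose already rest on the wrong metabolite. The documents do not support this. The by-code route gives correct numbers. The Part II condition is joined by AND to two cytokine conditions. The dose reviews drew on raw PGDM data.

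**Conclusion.** The table is wrong as written and should be corrected before the interim displays are produced. The extent is two of two urine rows, one analyte filed in the wrong tier (repeated in SAP 7.2.1), and one blister row whose name and code disagree.

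The consequence depends on the route. By code, it is a wrong label on a primary result. By name, it is the wrong analyte, and the error is then whatever difference exists between the two metabolites; the documents give no figure for that. An effect on Part II needs the by-name route, a participant who meets both cytokine conditions, and metabolites on opposite sides of 1.3x.

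This rests on the codes being right in the data, which is the likelier reading because the endpoint text uses the same letters. The documents cannot prove it. Nor do they settle whether the blister row is IP-10 or IL-10; its neighbours in the list suggest IP-10, but IL-10 is also measured in this study.

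**What to change.** - In SAP 10.3.3, pair TETPGDM with the D metabolite and file it as primary; pair TETPGEM with the E metabolite and file it as exploratory.
- In SAP 7.2.1, restrict the primary label on urine biomarkers to tetranor-PGDM.
- In SAP 3.2, name TETPGDM as the variable for the 1.3x criterion.
- Check the LC-MS urine transfer and the blister MSD transfer to confirm which analyte each code holds, including whether the blister row is IP-10 or IL-10. Then correct that row's name or code to match.

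All of this should be done before the interim displays are run. The cost is a few table cells, two small text edits and a one-off data check; no design or sample-size change is involved.
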